5.5 Exclusion Criteria

Women who meet any of the following criteria will be excluded from the study. Of note, the study is limited to premenopausal women with an intact uterus because the mucosal immune environment differs substantially between pre- and post- menopausal women. Therefore, inclusion of post-menopausal women would introduce heterogeneity into the population.

- 1.) Menopause (as defined as amenorrhea for one year or more without an alternative etiology)
- 2.) Hysterectomy
- 3.) Participant report of any of the following:
 - a) Known adverse reaction to any of the study products (ever)
 - b) Non- therapeutic injection drug use in the 12 months prior to Screening
 - c) Surgical procedure involving the pelvis in the 60 days prior to enrollment (includes dilation and curettage or evacuation, and cryosurgery; does not include cervical biopsy for evaluation of an abnormal pap smear)
 - d) Participation in a drug, spermicide and/or microbicide study in the 30 days prior to enrollment
 - e) Currently pregnant or pregnancy within 42 days prior to enrollment
 - f) Currently lactating
 - g) Use of a diaphragm, NuvaRing®, or spermicide for contraception
- 4.) Urogenital infection or suspected infection within 7 days of enrollment including: symptomatic candidiasis, trichomonas vaginalis, and symptomatic bacterial vaginosis; or cervical infection, including *N. gonorrhoeae* (GC), *C. trachomatis* (CT), or mucopurulent cervicitis; syphilis; HSV lesions, or other sores (Note: seropositive HSV without active lesions will not be excluded); acute pelvic inflammatory disease; urinary tract infection; recent exposure to a partner with GC, CT, Trichomonas, syphilis, or NGU
- 5.) Antibiotic or antifungal therapy (vaginal or systemic) within 7 days of enrollment
- 6.) As determined by the PI, has any significant uncontrolled active or chronic cardiovascular, renal, liver, hematologic, neurologic, gastrointestinal, psychiatric, endocrine *including poorly controlled diabetes), respiratory, immunologic disorder or infectious disease
- 7.) Menses-like bleeding at the time of the Enrollment visit* or expected menses-like bleeding within 14 days of the Enrollment visit
(*Women who have vaginal bleeding at the scheduled Enrollment visit may return at a different date to be re-examined and possibly enrolled provided they are still within the screening window and meet all criteria.)
- 8.) Any condition that, in the opinion of the Investigator, would preclude provision of consent, make participation in the study unsafe, complicate interpretation of study outcome data, or otherwise interfere with achieving the study objectives

6 STUDY PRODUCT

6.1 Regimen

Each participant will receive one vaginal film containing MK-2048 in either a high dose Eudragit® (12.8%) film or low dose Eudragit® (6.4%) film

6.2 Administration

After eligibility is confirmed, site staff will randomize the participant to one of two film formulations: high dose Eudragit® or low dose Eudragit®. The site staff will retrieve the film from the pharmacy.

To ensure appropriate placement, the clinician will place the film in the proximal third of the vagina using a speculum.

6.3 Study Product Formulation

Participants will be randomized to one of two formulations- high (12.8%) or low (6.4%) Eudragit® polymer. Both films contain 30mg of MK-2048. The films are 2" x2."

Calculated composition of MK-2048 30 mg extended release vaginal film (low ammonio methacrylate copolymer type B)

Component	Quantity (mg/film)	Function
MK-2048	30.0	API
Hydroxypropyl methylcellulose E5 (VIVAPHARM® HPMC E5, Hypromellose 2910)	36.7	Film forming polymer/base
Hydroxyethyl cellulose (HEC, NATRASOL™ 250L PHARM)	36.7	Film forming polymer/base
Hydroxypropyl methylcellulose (BENECEL™ K4M HPMC Type 2208)	45.4	Film forming polymer/base
Hydroxypropyl cellulose (HPC, KLUCEL™ JXF PHARM)	73.4	Film forming polymer/base
Ammonio methacrylate copolymer dispersion type B (Eudragit® RS 30D)a	41.5	Extended release polymer
Polyethylene glycol 400 (PEG 400)	39.3	Plasticizer/dispersant
Propylene glycol (PG)	28.7	Plasticizer/dispersant
Purified Water _b	11.0	Solvent
Total unit weight		

Calculated composition of MK-2048 30 mg extended release vaginal film high ammonio methacrylate copolymer type B)

Component	Quantity (mg/film)	Function
MK-2048	30.0	API
Hydroxypropyl methylcellulose E5 (VIVAPHARM® HPMC E5, Hypromellose 2910)	30.1	Film forming polymer/base
Hydroxyethyl cellulose (HEC, NATRASOL™ 250L PHARM)	30.1	Film forming polymer/base
Hydroxypropyl methylcellulose (BENECEL™ K4M HPMC Type 2208)	37.2	Film forming polymer/base
Hydroxypropyl cellulose (HPC, KLUCEL™ JXF PHARM)	60.3	Film forming polymer/base
Ammonio methacrylate copolymer dispersion type B (Eudragit® RS 30D)a	68.1	Extended release polymer
Polyethylene glycol 400 (PEG 400)	32.3	Plasticizer/dispersant
Propylene glycol (PG)	23.6	Plasticizer/dispersant
Purified Water _b	10.0	Solvent
Total unit weight	321.7	

6.4 Study Product Supply and Accountability

Study product will be manufactured and package by Benefit Coatings, Stratford, CT, in compliance with cGMP. Product release testing includes GMP Microbial Limits Testing (USP61/62). After product release, the packaged study product will be provided to the UPMC Magee-Womens Hospital Pharmacy. All study product will be available to the study staff through the Magee Pharmacy.

The Magee research pharmacist will maintain complete accountability records of all study products received for this protocol and dispensed to participants. Additional documentation will be required for study product returns, destruction (if applicable) and other related issues as outlined in instructions for DAIDS clinical trials. All unused study products must be returned to the Pharmacy after the study is completed or terminated.

The film is packaged into a foil-lined pouch and stored at room temperature of 20-25°C (68-77°F). GMP stability testing will be conducted for the clinical trial product material. Research and development level stability testing is available for the film and shows the product to remain within target specifications at all time points evaluated to date.

6.5 Study Product Dispensing

Study products will be dispensed to clinic staff only upon receipt of a written prescription signed by an authorized prescriber.

6.6 Concomitant Medications

Enrolled study participants may use concomitant medications during study participation. All concomitant medications, over-the-counter preparations, vitamins and nutritional supplements, recreational drugs, and herbal preparations will be recorded on the concomitant medications log form.

All participants will be counseled to avoid the use of spermicide and other non-study vaginal products (other than tampons during menstruation and female condoms) while participating in the study. Participants who report use of these products will be counseled regarding the use of alternative methods; however reported use of these products does not require any change in study product administration or follow-up procedures. Condoms, if provided by study staff, will not be coated with any type of spermicide.

7 STUDY PROCEDURES

This section describes visit-specific study procedures.

7.1 Pre-Screening

As part of participant outreach and recruitment strategies, study staff may pre-screen potential study participants (e.g. via telephone). During these interactions, study staff may explain the study to participants and ascertain elements of presumptive eligibility, to be confirmed at an on-site screening visit. If the participant is eligible based on a screening script her name and appointment time will be placed on the script. If she signs consent, the telephone script will then become part of her research record. If she does not sign consent, the form will be de-identified.

7.2 Visit 1: Screening Visit

Screening may take place up to 45 days prior to Enrollment. Screening procedures may occur over several visits. A combined written informed consent for screening and enrollment will be obtained before any screening procedures are initiated. For participants who do not meet the eligibility criteria, screening will be discontinued once ineligibility is determined.

The table below outlines procedure to take place at the Screening visit.

Table 1: Visit 1 Procedures

VISIT 1: SCREENING VISIT	
Component	Procedure/Analysis
ADMINISTRATIVE	
 • Written Informed Consent • Assign Study Number (PTID) • Review Eligibility • Collect Contact Information • Medical history and concomitant medications • Visit Questionnaire • HIV Pre-/Post-Test Counseling • Screening Results • Protocol counseling (including effective birth control, sexual practices restrictions and vaginal product use) • Schedule Next Study Visit, prn • Participant Reimbursement
URINE	
 • Pregnancy test • Urine dipstick, as clinically indicated
SALIVA	
 • Rapid HIV
BLOOD	
 • Confirmatory HIV, as clinically indicated
VAGINAL	
 • pH • Wet Mount, as clinically indicated • Trichomonas (NAAT) • Vaginal sample for Future Use*
CERVICAL	
 • GC/CT (NAAT) • Cervical sample for Future Use* • Pap smear, as indicated
CVL	
 • Levels of antiviral activity • Levels of glycoproteins and mucins • Levels of cytokines & innate immunity factors • Assessment of drug assay specificity for MK-2048 and Eudragit®
PHYSICAL EXAM	
 • Physical Exam • Vital Signs (BP) • Height & Weight
PELVIC EXAM	
 • Bimanual Exam, as clinically indicated • External Genital & Speculum Exam

* For participants who have consented to the collection of samples for future use and use of left-over samples for future studies.

7.3 Visit 2: Enrollment

Subjects who meet the inclusion and exclusion criteria following the Screening visit may schedule an Enrollment visit. Care will be taken to schedule the Enrollment visit at a time when the participant is not expecting to be actively bleeding or anticipating her menses within 14 days.

Before performing any enrollment procedures, study staff will confirm eligibility. The participant will undergo a pelvic examination. Pelvic specimens as described below will be collected and the study staff will assess for bleeding. If no bleeding or other exclusionary findings are evident, the participant will then be randomized to study product. The act of randomization is considered the

act of enrollment for this study. Subjects with menses like vaginal bleeding at the Enrollment visit will not be randomized/enrolled at that time. These subjects may be rescheduled if vaginal bleeding resolves before 45 days from Screening have elapsed. If vaginal bleeding does not resolve during the window period, and the subject expresses interest in enrollment for the study, she may be rescreened.

After eligibility is confirmed, the site staff will go to the Pharmacy to obtain the study product. The clinician will insert a speculum and then place the film in the proximal third of the vagina under direct visualization per the SOP. After film placement, participants will be scheduled for Visit 3. Participants who agree to optional additional PK sampling will undergo blood draw and blind vaginal swab sampling for drug levels at 1-2 time points within the first 6 hours post insertion.

Table 2: Visit 2 Procedures

VISIT 2: ENROLLMENT – DAY 0 (Day 1 of Product Use)	
Component	Procedure/Analysis
ADMINISTRATIVE	
 • Review/Confirm Eligibility • Collect/Update Contact Information • Visit Questionnaire • Update medical history and concomitant medications • Screening Results • Protocol counseling (including effective birth control, sexual practices restrictions and vaginal product use) • Assess/Document Adverse Events • Schedule Next Study Visit • Participant Reimbursement
ACCEPTABILITY	
 • Acceptability Questionnaire (post film insertion)
BLOOD	
 • Baseline MK-2048 level • Optional MK-2048 level *
URINE	
 • Pregnancy test • Urine dipstick, as clinically indicated
VAGINAL	
 • pH • Wet Mount, as clinically indicated • Gram Stain • Quantitative Vaginal Culture • Quantitative PCR for microbiota • MK-2048 level • Optional vaginal swab(s) for MK-2048 ** • Vaginal sample for Future Use***
CERVICAL	
 • Cervical sample for Future Use***
PHYSICAL EXAM	
 • Physical Exam, as clinically indicated • Vital Signs (BP)
PELVIC EXAM	
 • Bimanual Exam, as clinically indicated • External Genital & Speculum Exam
RANDOMIZATION	
 • Randomization to study product
STUDY PRODUCT	
 • Study Product Distribution • Clinician-inserted with speculum

*Participants may opt to have one additional blood draw at 1, 2, 3, 4, 5 or 6 hours post film insertion for MK-2048 levels.

**Participants may opt to have additional vaginal swabs collected at one or two time points (1, 2, 3, 4, 5, or 6 hours) post film insertion. The swabs will be collected by a clinician without a speculum.

***For participants who have consented to the collection of samples for future use and use of left-over samples for future studies.

7.4 Visit 3, 4, 5, 6, 7 and 8: Follow-Up Visits

Visit 3, 4, 5, 6, 7 and 8 procedures are outlined in Table 4. The windows around these study visits are as follows:

Visit 3: Day 3 (2-4)

Visit 4: Day 5 (5-6)

Visit 5: Day 7 (7-8)

Visit 6: Day 10 (9-12)

Visit 7: Day 14 (13-16)

Visit 8: Day 28 (24-32)

Two cervical biopsies will be obtained at Visit 5 only. A CVL will be performed at Visits 7 and 8. Residual drug, if present, will be removed during the CVL at Visit 7. The purpose of Visit 8 is to provide a final safety assessment.

Table 3: Follow-up Visit Procedures

VISIT 3, 4, 5, 6, 7, 8 FOLLOW-UP VISITS	
Component	Procedure/Analysis
ADMINISTRATIVE	
 • Collect/Update Contact Information • Visit Questionnaire • Update medical history and concomitant medications • Protocol counseling excluding Visit 8 (including effective birth control, sexual practices restrictions and vaginal product use) • Assess/Document Adverse Events • Schedule Next Study Visit (excluding Visit 8) • Participant Reimbursement
ACCEPTABILITY	
 • Acceptability Questionnaire (Visit 5 ONLY; prior to biopsy)
BLOOD	
 • MK-2048 level
URINE	
 • Pregnancy test (Visit 5 & 8 and as clinically indicated) • Urine dipstick, as clinically indicated
VAGINAL	
 • pH • Wet Mount, prn • Trichomonas (NAAT), as clinically indicated • Gram Stain • Quantitative Vaginal Culture • Quantitative PCR for microbiota • Vaginal swab for MK-2048 level • Vaginal sample for Future Use*
RECTAL	
 • Rectal swab for MK 2048 (Visit 5 ONLY)
CERVICAL	
 • GC/CT (NAAT), as clinically indicated • Cervical biopsies- two adequate (Visit 5 ONLY) • Cervical sample for Future Use*
CVL (Visits 7 and 8 only)	
 • Levels of antiviral activity • • Levels of glycoproteins and mucins • Levels of cytokines & innate immunity factors • MK-2048 level • Eudragit® levels
PHYSICAL EXAM	
 • Physical Exam, as clinically indicated • Vital Signs (BP)

PELVIC EXAM	
 • Bimanual Exam, as clinically indicated • External Genital & Speculum Exam
--------------------	--

* For participants who have consented to the collection of samples for future use and use of left-over samples for future studies.

7.5 Participants Who Become Pregnant

Urine pregnancy tests will be performed at screening, enrollment, Visit 5, Visit 8, and as clinically indicated. Participants who become pregnant will be referred for care. Should the pregnancy be diagnosed during study follow-up, pelvic exams will only be performed to evaluate a participant's reported symptom. No genital specimens will be collected in a pregnant participant.

Participants will be terminated from the study but will be contacted after their study participation to ascertain the pregnancy outcome.

Study staff will report pregnancy details to the Antiretroviral Pregnancy Registry should an enrolled participant become pregnant during follow-up.

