
2.2 Integrated Preclinical/Clinical Program

The Film Antiretroviral Microbicide Evaluation (FAME) program brings together an interdisciplinary group of research scientists from four academic institutions: University of Pittsburgh, University of Washington, Carnegie Mellon University, and the University of Colorado. The long-term goal of the program is to develop and evaluate an extended delivery vaginal film containing an integrase inhibitor which could provide protection from HIV for one week or more following a single application. The first iteration of the FAME IPCP established proof of concept that vaginal films containing the antiretrovirals (ARVs) dapivirine and tenofovir could deliver drug to target tissues as effectively as gel formulations of those same ARVs. The second iteration of the program featured FAME-101, a clinical trial which established proof of concept for the extended release placebo vaginal film. In FAME-101, 64 participants received a single dose of the extended release vaginal film and were randomized to the timing of follow-up (3,7,10 or 14 days). The extended release placebo film was well tolerated and visible in 56% of the participants randomized to follow-up at 7 days and 25% randomized to follow up at 14 days. The goal of the second iteration of the FAME IPCP is to leverage this extended release film platform to establish proof of concept that an extended release formulation of an antiretroviral drug could provide coverage for 7 days or longer after a single application. An extended release formulation could address the challenges associated with daily use of products which have undermined adherence, and therefore effectiveness, in clinical trials. For this proof of concept study, the integrase inhibitor MK-2048 will be evaluated in the extended release film formulation although the extended release film format could be used as a delivery method for a wide range of antiretroviral drugs.

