8.3 Adverse Events Definitions

An AE is defined as any untoward medical occurrence in a clinical research participant administered an investigational product and which does not necessarily have a causal relationship with the investigational product. As such, an AE can be an unfavorable or unintended sign (including an abnormal laboratory finding, for example), symptom or disease temporally associated with the use of an investigational product, whether or not considered related to the product. This definition is applied to all groups beginning from the time of randomization.

Study participants will be provided instructions for contacting the study site to report any untoward medical occurrences they may experience, except for possible life-threatening events, for which they will be instructed to seek immediate emergency care. Where feasible and medically appropriate, participants will be encouraged to seek evaluation at UPMC Magee-Womens Hospital, where the study clinicians are based, and to request that a study clinician be contacted upon their arrival. All participants reporting a clinically significant untoward medical occurrence will be followed either in person or by phone until the occurrence resolves (returns to baseline) or stabilizes over a four week period.

Study site staff will document AEs reported by or observed in enrolled study participants regardless of severity and presumed relationship to study product.

For each study participant, AE documentation and reporting will be undertaken throughout the scheduled duration of follow-up, i.e., through Visit 8.

The PI/designee will grade the severity of each AE and the relationship of the AE to study product:

AE severity will be graded per the DAIDS Table for Grading Adult and Pediatric Adverse Events, Version 2.1, July 2017 and the Female Genital Grading Table for Use in Microbicide Studies (Appendix 1, version 1.0, November 2007) except that asymptomatic BV will not be considered an AE. AEs not included in the Female Genital Grading Table will be graded by the DAIDS AE Grading Table Version 2.1, July 2017. In cases where a genital AE is covered in both tables, the Female Genital Grading Table for Use in Microbicide Studies will be the grading scale utilized.

The relationship of all reported AEs will be assessed based on the Manual for Expedited Reporting of Adverse Events to DAIDS (Version 2.0, dated January 2010) and the clinical judgment of the PI/designee.

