8.5.1 Product Hold

In the unlikely event that a participant is intolerant of the study product immediately after placement, the site clinician will perform a pelvic exam to remove all visible product.

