10.1.4 Pregnant women

Pregnancy is an exclusion criterion as the vaginal microenvironment in pregnancy differs substantially from the non-pregnant state. Including pregnant participants would make the interpretation of study results difficult. Women who become pregnant during the study period following randomization will be terminated from the study. Participants who become pregnant during the course of the study will be contacted periodically after study termination in order to determine the pregnancy outcome.

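### A dosed woman who exits early for pregnancy or HIV has no active AE follow-up to Visit 8, yet if seen at Day 7 she still counts in the primary safety proportion

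*Combined protocol and SAP*

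**What the plan says.** **Exit rules.** Section 7.5 schedules pregnancy tests after dosing at Visit 5 (Day 7) and Visit 8 (Day 28). For a positive result it states: "Participants will be terminated from the study but will be contacted after their study participation to ascertain the pregnancy outcome". Section 10.1.4 agrees: "Women who become pregnant during the study period following randomization will be terminated from the study". Both name the pregnancy outcome as the only purpose of later contact. Section 10.2.1 refers women diagnosed with HIV for care and exits them.

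**AE window.** Section 8.3 says that for each participant "AE documentation and reporting will be undertaken throughout the scheduled duration of follow-up, i.e., through Visit 8". It also follows reported clinically significant events, in person or by phone, until they resolve or stabilize. Section 8.7 asks for a best-effort final evaluation of anyone who leaves early, without saying what it contains.

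**Who counts.** Section 9.7.4 makes a woman evaluable if she completes screening and enrollment and attends Day 7 in window; only non-evaluable women are replaced. Section 9.2 expects 48 women evaluable for the primary endpoint, the proportion with a Grade 2 or higher AE. Section 9.7.2 has no rule for shortened follow-up.

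**Film.** Section 7.4 says: "Residual drug, if present, will be removed during the CVL at Visit 7". Section 8.5.1 provides for removal when a woman is "intolerant of the study product immediately after placement". In pregnancy, section 7.5 says "No genital specimens will be collected in a pregnant participant" and, on examinations, "Should the pregnancy be diagnosed during study follow-up, pelvic exams will only be performed to evaluate" a symptom that she reports. Section 2.2 gives persistence of the placebo film: "visible in 56% of the participants randomized to follow-up at 7 days and 25% randomized to follow up at 14 days". Section 2.4 adds 44% at Day 3 and identifies that film as the high Eudragit formulation.

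**The concern.** The plan promises AE ascertainment to Day 28 for everyone, but its exit rules remove some dosed women from the visits at which AEs are elicited. The Day 7 pregnancy test is the clearest case, because it is a scheduled event that can trigger termination three weeks before the AE window closes. The same visit makes the woman evaluable, so she is neither replaced nor dropped from the denominator. An event she has after exit and does not report is in effect counted as no event. The primary endpoint is safety, and section 10.2.1 describes this as the first time these films are tested in humans. A later change of analysis set could not recover AE data that were never collected.

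A separate gap concerns the product itself. The planned removal is at Day 14, and nothing says what happens to film remaining in a woman who leaves before then, or that its presence at exit is recorded.

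**Working it through.** **1. The plan's own precision figures.** The upper limit of the two-sided 95% exact (Clopper-Pearson) interval for x events in n women is the 0.975 quantile of Beta(x + 1, n − x).

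- 0/48 gives 7.4% (section 9.2: 7.4%).
- 5/48 gives 22.7% (section 9.2: 22.6%, a rounding difference).
- 3/24 gives 32.4% (section 9.2: 32.4%).

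The figures reproduce, and this point does not dispute them.

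**2. Following one woman through the sections.** She is dosed at Day 0, attends Day 7 in window and tests positive.

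- Section 9.7.4: evaluable, so not replaced.
- Sections 7.5 and 10.1.4: terminated; later contact is for the pregnancy outcome.
- Section 8.7: a final evaluation if possible, on one occasion.
- Section 8.3, follow-up to resolution: covers events already reported.
- Section 8.3, re-assessment after study exit: covers Grade 3 or higher or related AEs still ongoing at Visit 8.
- Section 8.3, AE window: documentation for each participant through Visit 8.

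None of the middle provisions looks for a new event between her exit and Day 28, so the last line has no stated means of being met.

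**3. Observation lost.** Exit at Day 7 with Visit 8 at Day 28 loses 28 − 7 = 21 days, and 21/28 = 75%; she contributes 7/28 = 25%. Across the visit windows in section 7.4 the loss runs from (24 − 8)/24 = 67% to (32 − 7)/32 = 78%.

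**4. Possible effect on the primary endpoint.** Let m evaluable women leave at Day 7, each with an unseen Grade 2 or higher AE. The documents give no pregnancy or dropout rate, so m is an assumption.

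| m | Full cohort, starting at 5/48 | Upper limit | One arm, starting at 3/24 | Upper limit |
|---|---|---|---|---|
| 0 | 5/48 | 22.7% | 3/24 | 32.4% |
| 1 | 6/48 | 25.2% | 4/24 | 37.4% |
| 2 | 7/48 | 27.8% | 5/24 | 42.2% |

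These are the outer values for each m. If the women who left had no event, nothing changes.

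**5. Film persistence.** The stated 44%, 56% and 25% fit 7/16, 9/16 and 4/16. Sixteen per group is an assumption (64 women over four follow-up groups); of the group sizes from 12 to 20, only 16 gives all three percentages. Exact 95% intervals are:

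- Day 3: 44% (20% to 70%).
- Day 7: 56% (30% to 80%).
- Day 14: 25% (7% to 52%).
- Days 3 and 7 pooled: 16/32 = 50% (32% to 68%).

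All are for the high Eudragit placebo film. There is no human persistence figure for the low film, which section 2.3 says dissolves faster in vitro, or for either MK-2048 film.

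**The case against.** **AE follow-up.** Early exit shortens follow-up in any trial, and section 8.3 speaks of the scheduled duration. No sentence says that AE collection stops at termination. Section 8.7 covers women who are withdrawn as well as those who withdraw, section 8.3 follows reported events to resolution, and section 10.1.4 plans periodic contact in pregnancy. A reader might infer that AE collection has ended for these women; the text does not go that far. What stands is that no provision actively seeks new events after exit. Incarceration is not simply another instance, because section 10.1.3 lets a released woman return for follow-up or safety visits.

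**Frequency.** Effective contraception is required, pregnancy is tested at enrollment, and abstinence runs from Visit 2 to Visit 7. Cases should be few, although abstinence after dosing cannot prevent a conception before it.

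**Film.** A speculum examination takes place at every follow-up visit, interim visits are allowed, and a pregnant woman with a symptom may be examined. Most leavers will therefore have had a recent examination. The case left open is mainly the asymptomatic woman found pregnant, in whom section 7.5 rules out both the examination and the lavage.

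**Conclusion.** The AE point holds as an inconsistency between the exit rules (7.5, 10.1.4, 10.2.1) and the AE window in 8.3. Its statistical consequence runs through 9.7.4: a woman seen at Day 7 can count in the Grade 2 or higher proportion with about a quarter of the planned observation. The bias, if any, is downward. The number of women is probably small and cannot be estimated from the documents; the limits of 25.2% and 27.8% assume one or two unseen events on top of 5/48.

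The film point holds only as a gap. Three stronger readings are tempting and unsupported:

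- That film is probably in place at exit. The 56% is for one placebo formulation, with an interval that includes 50%, and the Day 3 figure is 44%. The data support only that film may be in place.
- That early exit contradicts the Visit 7 removal step. Section 7.4 describes women who attend that visit and is silent on the others.
- That the 54 − 48 = 6 spare randomization places in section 9.6 predict how many women leave with film. They also cover unusable product and are not a dropout forecast.

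**What to change.** **AE ascertainment.** Amend sections 7.5, 8.7, 10.1.4 and 10.2.1 so that stopping study visits and specimens does not stop AE ascertainment. Collect AE history through Day 28, by visit or telephone, from every dosed woman who leaves early and agrees to contact. For pregnancies, use the contact already planned. In section 9.7, add a line reporting how many evaluable women in each arm had AE follow-up cut short of Visit 8.

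**Film.** Reconcile sections 7.4, 7.5, 8.5.1 and 8.7 for a dosed woman who leaves before Visit 7. The clinical rule is for the investigators to set. Whatever it is, record film status at the last examination already being performed.

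**Cost.** A wording amendment, one or two extra calls for a few women, and one added item on film status. The consent form may need a matching sentence. The downside is slight extra site work.
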